Confidentiality will be protected by collecting only information needed to assess study outcomes, minimizing to the fullest extent possible the collection of any information that could directly identify subjects, and maintaining all study information in a secure manner. Storage of all data will be electronically entered on a password protected network drive. To help ensure subject privacy and confidentiality, only a unique study identifier will appear on the data collection form. All question and answers will be recorded by research assistants, placed in confidential subject folders, and stored on a separate master log. Any collected patient identifying information corresponding to the unique study identifier will be maintained on a separate master log. The master log will be kept secure, with access limited to designated study personnel. Following data collection subject identifying information will be destroyed at the earliest opportunity, consistent with data validation and study design, producing an anonymous analytical data set. Data access will be limited to study staff. Data and records will be kept locked and secured, with any computer data password protected. No reference to any individual participant will appear in reports, presentations, or publications that may arise from the study.

Per copyright agreement for the Social Connectedness Scale-Revised (SCS-R), the PI has agreed to send de-identified results of the SCS-R and basic demographics to the author of the measure for possible secondary data analysis.

Conflict of Interest: There are no conflicts of interest.

Benefits to Participants

This study does not present the prospect of direct benefit to the participants. However, the study will provide the opportunity to gain a better understanding of how migraine affects pain processing.

PUBLICATION OF RESEARCH FINDINGS

We plan to publish our findings in top-tier scientific, peer-reviewed journals.

PART 2

PRÉCIS

Objectives

Primary objective: Test the impact of MBSR in adults with migraines on clinical headache pain.

Secondary Objectives: Test the impact of MBSR in adults with migraines on experimental heat pain, mindfulness, pain acceptance, pain catastrophizing, emotional reactivity, and headache-related disability compared to an education control group; determine factors that predict MBSR response on migraine pain.

Design and Outcomes

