cultivate a detached observation of sensory experiences like pain,^{49,74} which may alter the pain experience, resulting in less pain unpleasantness, pain catastrophizing, emotional reactivity, and more pain acceptance.^{45,59,60,62,63,77} The active mental training of meditation may also foster a non-reactive approach to life stressors. This may decrease emotional reactivity (e.g., affective responses to stress),⁵⁹⁻⁶³ thereby decreasing the likelihood of triggering a migraine from stress (a common migraine trigger).⁶⁴⁻⁶⁶ Further, meditation differentially decreases affective (pain unpleasantness) over sensory (pain intensity) response to experimental pain⁵⁰⁻⁵⁶ and engages brain regions important for the cognitive and affective modulation of pain.^{51,53,55-57,78,79} Based on this research and the models developed by Jensen,⁸⁰ Day et al,⁸¹ and Price,⁸² we created a simplified *theoretical* model of mechanisms of migraine pain relief from MBSR (**Figure 2**). By targeting affective/cognitive factors (**Figure 2, Box A**), we hypothesize that MBSR: A) prevents migraines from occurring, decreasing migraine frequency; B) decreases the affective components of pain so even when migraines do occur, pain unpleasantness is attenuated; and C) decreases migraine disability. (**Figure 2**). We will test these hypotheses directly by measuring both experimental and clinical pain.

Figure 2
Theoretical Model of MBSR Mechanisms of Migraine Pain Relief

MBSR also requires time, energy, and healthcare resources. Thus, identifying predictors of response is critically important to better target and tailor MBSR to treat migraine. For instance, pain acceptance and pain catastrophizing were the most important factors of treatment response of a mindfulness-based cognitive therapy for headache.⁸³ Since mindfulness meditation appears to selectively target these processes, we hypothesize that those with the highest baseline levels of pain catastrophizing, emotional reactivity, and the affective component of experimental pain will be most likely to respond to MBSR. Increases in pain acceptance and mindfulness and decreases in pain catastrophizing and emotional reactivity may be associated with decreases in clinical and experimental pain and disability after MBSR.

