No previous studies have used experimental pain to evaluate mechanisms of meditation on migraine. Measures of pain intensity and pain unpleasantness will assess nociceptive processing distinct from clinical pain status, providing a means to determine if clinical pain is differentially susceptible to reduction by MBSR. Further, employing experimental pain methodologies will allow us to distinguish affective from sensory processing, allowing us to test our hypotheses that MBSR reduces the affective more than the sensory experience, and this effect will be greater among patients with a greater affective component to their pain.

We will be able to determine predictors of MBSR response in migraineurs. Identifying simple and inexpensive ways to evaluate response will allow treatments to be targeted to those most likely to benefit.

PRELIMINARY STUDIES

We conducted several epidemiological studies that showed that many adults with neurological conditions, including headaches, use complementary and alternative medicine, despite a lack of evidence.⁸⁴⁻⁸⁹ Further, in adults with migraines/severe headaches in the US, the mind-body therapies of deep breathing, meditation, and yoga are the most commonly used.⁸⁸ However, there have only been a few prior studies with non-standardized meditation and yoga interventions in migraine.⁹⁰⁻⁹² We conducted 2 randomized controlled trials (RCT) of MBSR that demonstrated the safety, feasibility, and efficacy of MBSR in adults with mild cognitive impairment^{93,94} and migraines.⁵⁸ In 19 adults with migraines randomized to either MBSR (n=10) or usual care (n=9), MBSR demonstrated no adverse events, 0% dropout, excellent adherence (daily meditation average: 34±11 minutes; class average: 6/8 sessions), and promising effect sizes across several outcomes, despite being a pilot trial without adequate power (**Table 4**).⁵⁸ Theme analyses from qualitative interviews revealed that MBSR may also decrease emotional reactivity and improve pain cognitive reappraisal processes (e.g., less pain catastrophizing and more pain acceptance). The methods of this pilot trial⁵⁸ will be applied to this research. The results from this study support future studies with larger sample sizes to evaluate mechanisms.

Table 4: Improvements* in MBSR vs. Control Group after MBSR in Adults with Migraines

Measure	Change in MBSR vs. Control, d^f	95% CI^g	Comment
Headaches			Although underpowered, migraines were:

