Group: A risk to taking part in this study is the likelihood of receiving an intervention (that requires time and energy) that may not be effective in helping to treat migraines. The classes or other study-related procedures may cause some, all, or none of the side effects listed below.

Most Likely

Gentle stretching can cause muscle soreness if muscles have not been exercised in a long time. Sitting for extended periods of time can be uncomfortable. Chairs will be provided for comfort, and participants will be allowed to move as needed to relieve any discomfort.

Less Likely

With any activity, there is always a risk of injury. The instructor will advise the participants to avoid any posture that causes discomfort or pain. The instructor will be attuned to watching for any problems during each session.

Rare

There have been rare case reports of meditation or yoga causing a brief limited episode of psychiatric illness. However, most of these case reports are in individuals with a prior history of unstable psychiatric illness. There are no known reports of this occurring in anyone in an MBSR class. Having a history of unstable psychiatric illness is an exclusion criteria for participating in this project so therefore we have in place an extra precaution to not encounter this risk.

Description of alternative treatments and procedures. The alternative is to not participate in the study or to refer to the personal physician for standard treatment.

STATISTICAL CONSIDERATIONS

General Design Issues

To examine the hypotheses, we will again rely on mixed effects hierarchical regression models with a distribution and link function appropriate to the outcome (e.g., binomial distribution and logit link for daily migraine probability). These models will allow us to fully utilize all of the information (i.e., rather than simply calculating change scores) by conceptualizing each diary entry as nested within a diary phase (baseline 4 weeks prior to randomization, 8 weeks of treatment, and 3 and 6 months of follow-up), within a person (random effects), who is nested within a treatment group. Missing data will be scrutinized and we will utilize sensitivity analyses and/or multiple imputation as required. The models will be conducted as described below:

Hypothesis 2a: MBSR will decrease the primary outcome of migraine frequency compared to an education control group;

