Hypothesis 2b: MBSR will differentially affect the secondary outcome of the affective component (pain unpleasantness) of experimental heat pain compared to the education control group.

Hypothesis 2c: MBSR will improve the secondary outcomes of mindfulness, emotion regulation, pain acceptance, pain catastrophizing, and headache-related disability compared to an education control group.

Hypothesis 3A: High levels of baseline pain catastrophizing and emotional reactivity scores and high baseline levels of pain unpleasantness for experimental pain will predict the primary outcome response (migraine frequency) to MBSR.

Hypothesis 3B: Changes in mindfulness after MBSR will be directly associated with improvements in migraine frequency.

Sample Size and Randomization

Sample Size Calculation: For hypothesis 2a, using effect sizes from our pilot trial,⁵⁸ and by analyzing the data with our mixed effects hierarchical regression models, 44 participants/group (n=88) will provide >90% power with $\alpha=0.05$ to detect a difference of 1.3 migraine days/month over the course of the trial (used PASS design) (Hypothesis 2a). Hypothesis 2b has a similar power function as Part I of this study. For hypothesis 3: since hypothesis 3b is the most difficult to evaluate, this RCT is powered on this hypothesis. This calculation assumes a multivariable model examining linear changes with the four predictors (plus intercept and slope). A sample size of 88 participants will give us 80% power with effects as small as $R^2 \geq 6\%$ in the variance of the slopes; smaller predictors are unlikely to be clinically significant.¹⁰¹

Randomization: Once 4-week migraine logs are reviewed by study staff to ensure eligibility, participants will be randomized 1:1 to either MBSR or the education control group, stratified by migraine frequency (low frequency of 4-9 headaches/month or high frequency of 10-20 headaches/month). Treatment assignments will be generated by a permuted blocks method with randomly varying block size and sealed in numbered, opaque envelopes. [name] will generate the randomization (using the statistical SAS program "PROC PLAN" statement) and deliver the envelopes to the PI. Participants in both groups will continue to track their migraines with their daily REDCap logs for the duration of the trial.

Definition of Populations

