All the secondary outcomes and additional measures will be assessed with these standardized, reliable, well-validated instruments: Five-Facet Mindfulness Questionnaire (mindfulness),^{57,103} DERS (emotion regulation),^{3,104} PCS (pain catastrophizing),^{2,36} Chronic Pain Acceptance Questionnaire (pain acceptance),¹⁰⁵ Herth Hope Index (hope),¹⁰⁶ Life Orientation Test-Revised (optimism),¹⁰⁷ Headache Impact Test-6 (HIT-6) (headache related disability),¹⁰⁸⁻¹¹⁰ Migraine Disability Assessment (MIDAS)-one month (headache related disability),^{111,112} Patient Health Questionnaire-depression module, PHQ-9 (depression),³⁴ Generalized Anxiety Disorder-7, GAD-7 (anxiety),³⁵ Headache Management Self-Efficacy Scale (self-efficacy),¹¹³ Migraine Specific Quality of Life Questionnaire, version 2.1 (MSQv2.1) (quality of life),^{114,115} the Perceived Stress Scale 10, PSS (perceived stress),¹¹⁶ the Brief Resilience Scale, the Resilience Scale for Adults, the Flourishing Scale, the Social Connectedness Scale-Revised (SCS-R), the Pittsburgh Sleep Quality Index, the Allodynia Symptom Checklist (ASC-12), and well-validated NIH Patient Reported Outcomes Measurement Information System (PROMIS) measures of sleep, fatigue, pain interference, satisfaction with participation in social roles, and global health. Changes from baseline to initial follow-up will be primary outcomes; secondary outcomes will include changes from baseline to follow-ups at 3 and 6 months.

Additional Information Collected

Sociodemographic and clinical information will be collected at the screening visit.

Expectations for improvement: Expectations can impact results.^{39,117} At baseline and after the second session, participants will rate their expectations using the Credibility/Expectancy Questionnaire.⁹⁶

Class Attendance and Home Practice: Participants in both groups will track their home activities up to the 6-month follow-up visit via REDCap logs and the instructors will track patient class attendance.

Qualitative Interviews: At the initial follow-up, a 30-minute semi-structured interview will be conducted with participants to further explore areas not captured in our standardized quantitative measures.

Data Analyses

Analysis 2a: The probability that an individual experiences a migraine on any given day will be examined as a function of group (MBSR vs. control) and treatment phase. A statistically significant group x phase interaction will be interpreted as evidence that treatment differentially

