
impacted the daily probability of migraine. This effect size will be indexed by converting the daily probability to headache counts as recommended for clinical trials in headache.¹¹⁸ If necessary we will model change using polynomial trajectories (i.e., growth curves) to better fit the time-course of treatment.

Analysis 2b: To examine this hypothesis, we will conduct an ANCOVA with pain unpleasantness at post-treatment as the dependent variable, group as the independent variable, and pain unpleasantness at pre-treatment as the covariate.

Analysis 2c: This analysis is identical to 2b, with the appropriate outcomes.

Analysis 3a: Baseline levels of pain catastrophizing and emotional reactivity will be used as predictors in the multilevel models predicting the trajectory of migraine attacks over the course of treatment.

Analyses 3b: This analysis is similar to 3a, except that changes in mindfulness (i.e., change scores from pre-treatment to post-treatment) will be used as predictor of migraine trajectory.

DATA COLLECTION AND QUALITY ASSURANCE

Data Collection Forms

Information will be collected from REDCap daily headache logs for appropriate diagnosis of migraines during an initial 4 week period prior to randomization and participants will continue to track daily headaches for the duration of the trial. Ipod touches with Pendragon software will be available to those without internet access and unable to use REDCap from home. Experimental heat measurements will be conducted at baseline and at each of the 3 follow-up evaluations. Participants will also complete standardized questionnaires using REDCap at baseline and at each of the 3 follow-up evaluations with an option to complete these questionnaires at home prior to the visit. In addition, a 30 minute qualitative interview will be conducted at the first follow-up visit to evaluate the participants' experience with the interventions. Each interview will be audiotaped. Socio-demographic and clinical information will also be collected at the screening visit.

Description of data that will be recorded on human subjects. Each 30 minute qualitative interview of the migraine and control subjects will be audiotaped and then transcribed. Participants will be photographed one of the study visits. These photos will be stored on the study's secure Ishare. Each subject will have provided informed consent to perform this.

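### Analysis 3a does not test Hypothesis 3A: it states no predictor-by-group-by-time term and leaves out baseline experimental pain unpleasantness

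*Combined protocol and SAP*

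**What the plan says.** The aim appears in several places in Part 2. The secondary objectives include to "determine factors that predict MBSR response on migraine pain". The Study Rationale expects that patients having the "highest baseline levels of pain catastrophizing, emotional reactivity, and the affective component of experimental pain will be most likely to respond to MBSR". It adds a practical purpose: "Identifying simple and inexpensive ways to evaluate response will allow treatments to be targeted to those most likely to benefit". Hypothesis 3A, under General Design Issues, lists baseline catastrophizing and emotional reactivity, and then says that "high baseline levels of pain unpleasantness for experimental pain will predict the primary outcome response (migraine frequency) to MBSR".

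The matching entry under Data Analyses is one sentence. Analysis 3a states that "Baseline levels of pain catastrophizing and emotional reactivity will be used as predictors in the multilevel models predicting the trajectory of migraine attacks" during treatment. It names two predictors, does not say which arms are included, and names no interaction.

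No other section supplies the missing term:
- General Design Issues describes diary entries "nested within a diary phase (baseline 4 weeks prior to randomization, 8 weeks of treatment, and 3 and 6 months of follow-up", within person, within treatment group.
- Analysis 2a names a group x phase interaction, with no baseline predictor in it.
- Analysis 3b is defined by reference back: "This analysis is similar to 3a, except that changes in mindfulness" serve as the predictor.
- Sample Size and Randomization powers hypothesis 3 on 88 participants, for a model of linear change with four unlisted predictors, and mentions no interaction.

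Heat pain testing is scheduled at baseline (Table 8; Data Collection Forms), so the third predictor will be available.

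**The concern.** The hypothesis concerns differential benefit: does a high score mark people who gain more from MBSR than they would have gained from the education control? The analysis asks whether a high score forecasts the migraine course. Regression to the mean, natural course and attention can all make a baseline score forecast change in both arms alike. The education control is designed to match time, attention and expectation. An analysis of response that makes no contrast with it gives up that advantage.

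Two things are at stake. A factor that is merely prognostic could be reported as showing who should be offered MBSR, which is the use the Study Rationale has in mind. And one of three hypothesised predictors, the affective component of experimental pain, has no stated test. Analysis 2b uses pre-treatment unpleasantness only as a covariate for post-treatment unpleasantness, so it does not fill the gap.

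**Working it through.** **The plan's own figure.** The sample size section gives 80% power for hypothesis 3 with 88 participants at an R2 of 6% of slope variance. A noncentral F test (1 df, four predictors, two-sided 0.05, n = 88) gives 64.9%. About 80% is reached if the other predictors already explain roughly 30% of slope variance (81.0%), a value the plan does not give. The point here does not rest on this. It matters only because that statement describes no interaction.

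**Predictor lists side by side.** Hypothesis 3A and the Study Rationale: catastrophizing, emotional reactivity, experimental pain unpleasantness. Analysis 3a: catastrophizing, emotional reactivity. Three against two.

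**What each form of 3a can detect.** Take person-level change = b(arm) × x + arm effect + error, with x and error standard normal and 44 per arm (88 at 1:1), two-sided 0.05. As an illustrative slope, treat the R2 of 6% as belonging to one predictor within an arm: b = √(0.06/0.94) = 0.253. This borrows a figure set for a different model.

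Let b be equal in both arms, so that the factor is prognostic and says nothing about MBSR. By normal approximation:
- Pooled: SE = 1/√88 = 0.107; 0.253/0.107 ≈ 2.37; chance of significance ≈ Φ(2.37 − 1.96) ≈ 66%.
- MBSR arm only: SE = 1/√44 = 0.151; 0.253/0.151 ≈ 1.68; Φ(1.68 − 1.96) ≈ 39%.
- Interaction: the true slope difference is 0, so 5%.

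Simulation (60,000 trials per scenario) gives slightly lower values. The range over assumed slopes is:

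| Equal slope in both arms | Pooled | MBSR only | Interaction |
|---|---|---|---|
| 0.15 | 28% | 16% | 5% |
| 0.253 | 63% | 37% | 5% |
| 0.30 | 77% | 48% | 5% |
| 0.40 | 95% | 72% | 5% |

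Carrying group x phase over from Analysis 2a corresponds here to adding an arm term. At 0.253 the pooled rate is 63.3% without it and 63.6% with it.

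The error also runs the other way. With slopes of −0.3 in control and +0.3 under MBSR, the pooled test is significant in 6% of trials and the interaction in 77%.

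A check at diary level used 28 baseline and 56 treatment days, with an assumed mean daily probability of 0.3, person SD of 0.6 and latent change SD of 0.5 or 1.0 on the logit scale. The equally prognostic factor was flagged in 35% to 51% pooled and 20% to 28% in the MBSR arm alone, against 5% with the interaction.

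**What the interaction costs.** For an effect of 0.253 under MBSR only, SE = √(2/44) = 0.213; 0.253/0.213 ≈ 1.19; Φ(1.19 − 1.96) ≈ 22% (simulation 21%). The pooled test also gives 21%; the MBSR arm alone gives 37%. The 95% CI half-width is t(0.975, 84) × √(2/42) = 0.434 SD of change per SD of predictor.

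**The case against.** **Silence is not a specified wrong model.** Analysis 3a is one sentence and sets out no fixed effects in full, and the multilevel models it points to are built around treatment group. This stands in part. A reader might infer that the plan has deliberately excluded the interaction, and the text does not show that. But 2a states both its interaction and how it will be read, whereas nothing equivalent is given for 3a, so an analyst following the text would not test moderation.

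**The omitted predictor may be a slip.** The sample size section refers to four predictors. The three in Hypothesis 3A plus change in mindfulness would make four. The four are not listed, so this is inference, but it makes a drafting omission more likely than a decision to drop unpleasantness. The two sections still disagree.

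**The arms are probably pooled.** Powering hypothesis 3 on 88 points that way, which gives the MBSR-only figures less textual support. Pooling without the interaction does not cure the problem.

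**A single phase contrast might seem to be prescribed.** A reader might infer this from "Changes from baseline to initial follow-up will be primary outcomes". That sentence closes a paragraph on questionnaire measures and is not clearly about diary migraine days. Analysis 3a and the power text speak of trajectories, linear change and slopes, and Analysis 2a allows growth curves. The documents do not dictate one contrast.

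**The interaction has little power.** True. That is a reason to report imprecision, not to answer a different question.

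**Conclusion.** Both mismatches can be read from the text and need no simulation. As written, Analysis 3a could credit MBSR with a predictor that works equally in both arms, and it leaves one named predictor without a stated test.

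The percentages are illustrations. The slopes, residual scale and diary parameters are assumptions, and the R2 of 6% is borrowed from a power statement set on hypothesis 3b. It would be wrong to infer that this trial has a 63% chance of a false predictor: the documents do not show that any of the three factors is prognostic. Nor do they set a rule for selecting patients for treatment. The consequence is a possibly wrong or missing conclusion on a secondary objective, and primary analysis 2a is untouched. The correction is worth making because the stated analysis and its hypothesis ask different questions.

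**What to change.** Rewrite Analysis 3a as follows.

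- Fit both arms together. Make predictor x group x time the test of Hypothesis 3A, or predictor x group x phase, on the same time scale as the planned trajectory model.
- Apply it to catastrophizing, emotional reactivity and baseline experimental pain unpleasantness, and list the four predictors that the sample size section has in mind.
- Report each interaction with a 95% confidence interval and label the analysis exploratory. Three unadjusted 1-df tests carry a 13% to 14% chance of at least one false positive.
- Describe predictor main effects as prognostic only.
- Do not apply the hypothesis 3 power statement to the interaction.

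The cost is analysis text only, since every measure is already scheduled. The price is precision. With 44 per arm, about 80% power needs a slope difference of about 0.61 to 0.62 SD. At an MBSR-only R2 of 6% it would need about 250 per arm. A null interaction will therefore say little. The change buys specificity, not sensitivity.
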